5.4 Strategies for Recruitment and Retention

Appropriate patients will be invited to participate by the cardiologist during the visit. They will be given a study information flyer and contact information of the PI, who will screen for inclusion/exclusion criteria. The informatics team at NYU Langone may also provide a list of patients on a monthly basis who achieve < 50% of recommended PA. This will facilitate recruitment in the event of virtual visits when the patient fills out the PAVS via MyChart.

The PI will contact the individual cardiologist by email to inform them of the intent to recruit their patient into the remote monitoring study. If the cardiologist has any objections, they can inform the PI. The 'Friendly' Letter to the Provider is attached. If met, the PI will enroll them in the study. If the PI is not immediately present in the Center, the interested patient will be given the PI contact information. The PI will also access the expertise of the NYU School of Medicine CTSI Recruitment and Retention Unit as needed for both recruitment and retention. Description of the study and consent for participation will take place in one of the offices in the Preventive Cardiology Center. The PI may also describe the study over the phone to patients who call after being referred by their cardiologist.

Retention strategy: While subjects are wearing the Fitbit they will be contacted the first week to check in and see if they have any questions. They will be contacted as needed over the 3 months if the PI or RA notice they are not wearing the Fitbit daily to troubleshoot ideas to improve their Fitbit wear time.

Our target sample size is 59 subjects. Our target is to enroll 2-3 subjects per week. When the PI or RA is not present in the clinic, a study flyer will be left with the cardiologists and staff.

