5.9.3 Assessment of Subject Compliance with Study Intervention

If the patient subject has less than 5 days of valid Fitbit wear (less than 10 hours/day) for the week, the PI or RA will call the patient subject and discuss strategies to improve adherence. We will utilize the resources of the NYU Recruitment and Retention Unit as needed. We will follow up with the patient subjects with the method they prefer (phone, email, text) for Fitbit data collection and to schedule the follow-up data collection at 3 months.

6 Study Procedures and Schedule

Baseline visit: After their visit with their cardiologist, interested patient subjects will have the study described and consent and enrollment in the study if desired. Baseline data collection will take place. For the next 3 months the patient subject is asked to wear the Fitbit and sync to their app on their phone. At 3 months patient subjects will return to the clinic for follow-up assessment.

A sample of 10 patient subjects will be asked to provide feedback about the study at this follow-up visit. A semi structured interview guide will be used to obtain feedback about the intervention from their perspective. Upon study completion, qualitative interviews using a semi-structured interview guide with the three cardiologists and the one nurse practitioner in the Center who works with one of the cardiologists will explore the acceptability, clinical utility and usability of the implementation.

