Phase 2. Each patient in the Center is seen by the medical assistant for the assessment of their vital signs and confirmation of the PAVS completion in the check-in kiosk. During the patient's visit with the cardiologist, an EHR decision support tool will be presented as an alert to the cardiologist for patients who are not achieving at least **50%** of recommended PA levels. This threshold was chosen for two reasons. A higher threshold (e.g. < 90%) would create many more alerts for the cardiologist and possibly lead to 'alert fatigue'. Second, our focus will be on the least active patients. The cardiologist will choose and acknowledge the PA promotion recommendations they discussed with the patient: #1) patients with a diagnosis appropriate for cardiac rehabilitation³⁰ will be given a suggested verbal referral to cardiac rehabilitation services; and/or #2) patients who are not eligible for a cardiac rehabilitation referral (or do not want to attend) will be given a verbal recommendation to start engaging in PA, or increase intensity and/or duration of PA with an agreed upon goal for the next 3 months. Patients who should not increase PA due to certain medical diagnoses (e.g. aortic stenosis, unstable angina) will be excluded. The cardiologist will inform these patients about the remote PA monitoring. Upon contact, the PI will describe the study, and if patients agree to participate, obtain consent, enroll the participant and collect baseline data. The PI will give participant a Fitbit Zip, set up an account with a study ID and ask them to wear the Fitbit Zip during all waking hours. NYU Langone has implemented integration of Fitbit Zip data into the EHR which requires the patient to sync their Fitbit account to the patient portal (MyChart) once and step counts will then sync to EHR and can populate the cardiologists' note. Participants will be given the first compensation for their time (\$50 gift card) at completion of this baseline visit. One week after enrollment, a follow-up call will be made to the participants to answer questions. The PI will review the PA data weekly to ensure that participants are correctly wearing the Fitbit Zip and data are being downloaded and synced. The PI will make follow-up reminders as needed. Data will be downloaded from each participant's record at the end of three months. At three months, the PI will meet with the participant to collect follow-up data and provide the second incentive of \$50. Qualitative interviews to assess the acceptability of the intervention (including previous use of smart devices) will be collected in a purposive sample (n=10) of participants with varying levels of PA and varying degrees of adherence to the Fitbit Zip. The participant may keep the Fitbit. In the event virtual recruitment and data collection is needed due to Covid-19 restrictions, or to minimize the amount of in-person time involved for the consent, the PI will discuss the study by telephone with the interested patient. If they meet inclusion criteria they will be sent via email an electronic link to the consent on REDCap (REDCap consent link attached). The PI will discuss the study and review the consent with the interested patient by telephone page by page. If the patient is interested in participation, they can electronically sign their consent.

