General health-related quality of life will be measured by the common data element 36-Item Short Form Health Survey (SF-36) v-1, a reliable measure ($\alpha = .90$) of physical and mental health with strong criterion validity, which is also available in Spanish.⁷⁷⁻⁸⁰ PROMIS surveys will be scored using the REDCap auto score for accuracy.

Clinical data will be collected from the EHR including potential confounding variables: age, sex, race/ethnicity, primary diagnosis, smoking status, and comorbidities (summarized as continuous data by the Charlson Comorbidity Index).⁴⁰

Sociodemographics, collected using common data elements survey⁴¹ and clinical data from the EHR will be collected at baseline. Fitbit steps will be collected daily for 3 months.

All other data will be collected baseline and at 3 months.

In the event all data collection must be remote or the subject prefers remote data collection, the PI will use baseline data from the electronic health record. The six-minute walk test can be administered remotely via an app on the subject's mobile phone with the distance walked emailed to the PI. BMI and blood pressure taken on the day of their recent clinical visit will be used for baseline data. A measuring tape will be mailed to the participant with instructions on measurement of waist circumference using standard technique. The PI or RA can schedule a videoconference to review the technique of measuring waist circumference. The most recent total cholesterol, HDL, and triglycerides results from the EHR will be used. All other baseline data collection will remain as planned.

If at 3-months remote data collection continues for a subject, the six-minute walk test will be done remotely with the mobile app. BMI and blood pressure will be used from the most recent office visit, as close to the 3-month follow-up date as possible. The patient will measure waist circumference as directed using standard technique and reviewed via video conference. The next available lab data for total cholesterol, HDL and triglycerides will be used. All other 3-month data collection will remain as planned.

If at 3-months in-person data collection is possible, the PI will resume in-person data collection as planned and meet the subject at the preventive cardiology center for data collection.

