6.1.4 Enrollment/Baseline

Enrollment/Baseline Visit (Visit 1, Day 0)

- Obtain informed consent of potential participant verified by signature on study informed consent form or on the REDCap electronic consent form.
- Verify inclusion/exclusion criteria.
- Obtain demographic and clinical information
- Collect baseline data (surveys, fingerstick lipids, six-minute walk test, waist circumference, body mass index)

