6.1.5 Final Study Visit

Final Study Visit (Visit 2; 3 months after baseline visit +/- 2 weeks)

- Record adverse events as reported by participant or observed by investigator.
- Collect follow-up data (surveys, fingerstick lipids, six-minute walk test, waist circumference, body mass index)

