7.3 Time Period and Frequency for Event Assessment and Follow-Up

The occurrence of an AE or SAE may come to the attention of study personnel during study visits and interviews of a study participant presenting for medical care, or upon review by a study monitor. All AEs including local and systemic reactions not meeting the criteria for SAEs will be captured on the appropriate RF. Information to be collected includes event description, time of onset, clinician's assessment of severity, relationship to study product (assessed only by those with the training and authority to make a diagnosis), and time of resolution/stabilization of the event. All AEs occurring while on study must be documented appropriately regardless of relationship. All AEs will be followed to adequate resolution.

Any medical condition that is present at the time that the participant is screened will be considered as baseline and not reported as an AE. However, if the study participant's condition deteriorates at any time during the study, it will be recorded as an AE. UPs will be recorded in the data collection system throughout the study.

Changes in the severity of an AE will be documented to allow an assessment of the duration of the event at each level of severity to be performed. AEs characterized as intermittent require documentation of onset and duration of each episode.

The PI will record all reportable events with start dates occurring any time after informed consent is obtained until 7 (for non-serious AEs) or 30 days (for SAEs) after the last day of study participation. At each study visit, the investigator will inquire about the occurrence of AE/SAEs since the last visit. Events will be followed for outcome information until resolution or stabilization.

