7.4.1 Adverse Event Reporting

Protocol for Adverse Events. If a patient participant experiences an adverse event during physical activity (e.g. experiencing a fall or musculoskeletal injury), they will be instructed to contact their physician immediately. If the event is an emergency that requires immediate medical attention (e.g. chest, jaw or arm pain, severe shortness of breath, rapid heart rate) they will be instructed to activate the emergency response system (e.g. call 911). The PI will monitor all reports of adverse events or serious adverse events related to this intervention. In the event an adverse or serious adverse event occurs, this will be reported immediately to the Data Safety Monitoring Board, the NYU IRB and to the sponsoring agency. A thorough investigation will be initiated, including review of the protocol to insure no undue exposure to risk occurred.

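### No adverse-event question is scheduled between day 0 and month 3, and no step carries an event from the cardiologist to the PI, so events may reach the PI and DSMB late or be missed.

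*Combined protocol and SAP*

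**What the plan says.** Section 7.3 sets the enquiry rule: "At each study visit, the investigator will inquire about the occurrence of AE/SAEs since the last visit". Sections 6.1.4 and 6.1.5 define two visits, at day 0 and at 3 months +/- 2 weeks. Only the second lists a safety task: "Record adverse events as reported by participant or observed by investigator". The Schedule of Events (Section 18) has no adverse-event row.

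The contacts between visits have other stated purposes. Section 6.1.1 says "One week after enrollment, a follow-up call will be made to the participants to answer questions". Under Section 5.9.3, when weekly Fitbit wear is too low, "the PI or RA will call the patient subject and discuss strategies to improve adherence".

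For an event during activity, Section 7.4.1 says of participants that "they will be instructed to contact their physician immediately". Section 7.1 similarly directs them to their cardiologist, or to emergency services if the event is severe. Section 7.4.1 has the PI monitor reports of events but does not say how a report travels from the cardiologist to the PI. The Measures part of Section 6.1.1 says "clinical data from the EHR will be collected at baseline", and the Schedule of Events marks EHR clinical data at baseline only.

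Section 5.7.2 does provide for a safety enquiry when a participant withdraws.

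**The concern.** Participants have cardiovascular disease or its risk factors, report less than half the recommended activity, and are advised to do more. Section 2.2.1 acknowledges that activity carries risk. The weeks in which they act on that advice are the weeks with no scheduled safety question.

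Two things are at stake.

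- **Completeness and timing of counts.** The review described in Section 7.6 responds to numbers and frequency of events. The 24- and 72-hour limits in Section 7.5 start at site awareness, so they put no limit on time spent before anyone at the site knows.
- **Quality of the event record.** Section 7.3 asks for time of onset, changes in severity, and the onset and duration of each intermittent episode. Without interim questions, these would rest largely on recall at 3 months. Recall is weakest for the minor falls and musculoskeletal injuries that Section 7.4.1 gives as examples.

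A drop in Fitbit wear may also be an early sign of illness or injury. The plan already detects it each week but does not say to ask about it.

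**Working it through.** **1. Count of enquiries.** Each planned contact, with its stated purpose:

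- Day 0 (6.1.4): consent, eligibility, baseline data. No safety item.
- Week 1 (5.4, 6.1.1): call to deal with questions. Safety not named.
- Weekly (6.1.1): PI review of Fitbit wear and syncing. Safety not named.
- Any week with fewer than 5 valid days (5.9.2, 5.9.3): contact about adherence. Safety not named.
- 3 months +/- 2 weeks (6.1.5): adverse events recorded.
- Withdrawal, if it occurs (5.7.2): adverse events asked about.

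Scheduled enquiries strictly between day 0 and the final visit: 0. Scheduled enquiries covering the activity period: 1.

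**2. Length of the gap.** Taking 3 months as 13 weeks = 91 days, the visit window gives 91 - 14 = 77 to 91 + 14 = 105 days.

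**3. Mean wait to enquiry.** Assumption: events fall evenly over the period. With one enquiry at its end, the mean wait is half the period: 13/2 = 6.5 weeks (45.5 days). Across the window it is 77/2 = 38.5 to 105/2 = 52.5 days.

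With several enquiries separated by gaps g, the mean wait is (sum of g squared) / (2 x 13):

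- Weeks 1 and 13 (gaps 1, 12): (1 + 144)/26 = 5.6 weeks.
- Weeks 1, 4, 8 and 13 (gaps 1, 3, 4, 5): (1 + 9 + 16 + 25)/26 = 51/26 = 1.96 weeks.

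So a question on the week-1 call alone shortens the mean wait only a little. The non-wear contacts cannot be put into this formula because they occur only when wear falls, and the documents give no rate for that.

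**4. Participants who may miss the final visit.** Section 5.6 gives 59 enrolled, 47 evaluable and about 20% attrition. This reproduces: 47/0.80 = 58.75, rounded up to 59, and 59 x 0.80 = 47.2. The difference is 59 - 47 = 12. The documents do not divide these 12 into withdrawals, who are asked under Section 5.7.2, and people lost without contact, who cannot be. The number never asked is an unknown part of 12.

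**The case against.** The best defence is that the plan has more routes to awareness than the visit rule suggests. Section 7.3 says events may come to light when a participant presents for medical care or on review by a monitor. The study site is the same cardiology center whose cardiologists participants are told to call, and those cardiologists are consented. Site and study clinician are not defined, so a call to the cardiologist could count as site awareness. Section 7.7 also calls for a site data and safety-monitoring plan, which is not among these documents and may hold the operational detail.

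Much of this stands, and it rules out several stronger conclusions that a reader might draw:

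- *Participants are asked only once, and events never reach the PI.* Section 5.7.2 adds the withdrawal enquiry, and Section 7.3 allows other routes.
- *The calls exclude safety, so someone who stops wearing the Fitbit after an injury is not asked why.* No call script appears in the documents. They are silent on the question and do not bar it.
- *Twelve participants go unasked.* Attrition is not split into withdrawal and silent loss.
- *The safety record will be falsely clean.* No figure in the documents supports that certainty.
- *Harm follows from accrual.* "Our target is to enroll 2-3 subjects per week" implies 2 x 13 = 26 to 3 x 13 = 39 of 59 enrolled when the first participant reaches week 13. That describes pace, not missed events.

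The defence does not close the gap. The routes in Section 7.3 are possibilities, with nobody assigned to pass events on. PI monitoring of reports presupposes that reports arrive. Consulting the cardiologist under Section 7.2.2 concerns expectedness once an event is known. Under Section 5.9.2 the monthly Epic report covers PAVS completion and referrals. The 3-month values taken from clinic records in remote follow-up are BMI, blood pressure and lipids.

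**Conclusion.** The point holds as a weakness of design. Followed as written, the plan leaves about 13 weeks (77 to 105 days) to one scheduled recall question, apart from the enquiry at withdrawal, and specifies no path from the cardiologist to the PI. Events may reach the PI and DSMB late or be missed. Minor falls, musculoskeletal injuries and events in participants lost without contact are the most exposed.

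The 6.5-week mean wait assumes evenly spread events and a 13-week period. It measures delay to the scheduled enquiry. Delay to awareness may be shorter and cannot be estimated from the documents. How many events would be missed cannot be estimated either. The change should be made because it costs little and the contacts already exist. The instruction to call the cardiologist is not at fault; what is missing is the onward notification.

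**What to change.** Amend Sections 5.9.3, 6.1.1 and 7.3 and the Schedule of Events as follows:

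- Add a fixed AE/SAE question to the week-1 call.
- Add the same question to every Fitbit non-wear contact, asking whether illness or injury is the reason.
- State how participating cardiologists notify the PI of events reported by enrolled participants.
- Ask participants to inform the study team as well. Leave the clinical instruction on whom to call unchanged.
- Add an adverse-event row to the Schedule of Events.

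Optional additions are brief messages at chosen interim points and an EHR check at 3 months for encounters since baseline. Weeks 4 and 8 are one example, at 2 x 59 = 118 messages. They bring most of the reduction in scheduled delay, from 5.6 to 1.96 weeks, but the exact weeks are a matter of choice. The EHR check should cover only participants whose authorization remains in force, because Section 12.4 limits use after revocation to information already collected.

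The core change uses existing contacts, so its cost is slightly longer calls and a few more minor events to record. The notification step gives the cardiologists, who are consented participants, a new duty, so check whether their consent form needs revision.

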7.4 Reporting Procedures – Notifying the IRB

Adverse Events. We do not anticipate any life-threatening adverse events for this proposed research project. In the event an adverse event or serious adverse event occurs, this will be reported immediately to the Data Safety Monitoring Board, the NYU IRB and to the sponsoring agency. A thorough investigation will be initiated, including review of the protocol to insure no undue exposure to risk occurred.

CONFIDENTIAL

This material is the property of the NYU School of Medicine and Langone Medical Center. Do not disclose or use except as authorized in writing by the study sponsor
Interventional Template Version: 11 January 2019

7.4.1 Adverse Event Reporting

Protocol for Adverse Events. If a patient participant experiences an adverse event during physical activity (e.g. experiencing a fall or musculoskeletal injury), they will be instructed to contact their physician immediately. If the event is an emergency that requires immediate medical attention (e.g. chest, jaw or arm pain, severe shortness of breath, rapid heart rate) they will be instructed to activate the emergency response system (e.g. call 911). The PI will monitor all reports of adverse events or serious adverse events related to this intervention. In the event an adverse or serious adverse event occurs, this will be reported immediately to the Data Safety Monitoring Board, the NYU IRB and to the sponsoring agency. A thorough investigation will be initiated, including review of the protocol to insure no undue exposure to risk occurred.

7.4.2 Serious Adverse Event Reporting

The protocol for serious adverse events will follow the same protocol for adverse events. If the event is an emergency that requires immediate medical attention (e.g. chest, jaw or arm pain, severe shortness of breath, rapid heart rate) they will be instructed to activate the emergency response system (e.g. call 911). The PI will monitor all reports of adverse events or serious adverse events related to this intervention. In the event an adverse or serious adverse event occurs, this will be reported immediately to the Data Safety Monitoring Board, the NYU IRB and to the sponsoring agency. A thorough investigation will be initiated, including review of the protocol to insure no undue exposure to risk occurred.

7.4.3 Unanticipated Problem Reporting

Incidents or events that meet the OHRP criteria for UPs require the creation and completion of an UP report form. It is the site investigator's responsibility to report UPs to their IRB and to the DCC/study sponsor. The UP report will include the following information:

- Protocol identifying information: protocol title and number, PI's name, and the IRB project number;
- A detailed description of the event, incident, experience, or outcome;
- An explanation of the basis for determining that the event, incident, experience, or outcome represents an UP;
- A description of any changes to the protocol or other corrective actions that have been taken or are proposed in response to the UP.

To satisfy the requirement for prompt reporting, UPs will be reported using the following timeline:

- UPs that are SAEs will be reported to the IRB and to the DSMB/study sponsor within 1 day of the investigator becoming aware of the event.
- Any other UP will be reported to the IRB and to the DSMB study sponsor within 2 days of the investigator becoming aware of the problem.
- All UPs should be reported to appropriate institutional officials (as required by an institution's written reporting procedures), the supporting agency head (or designee), and OHRP within<insert timeline in accordance with policy> of the IR's receipt of the report of the problem from the investigator.

